6.2.5. Storage

All study treatments must be stored in a secure, environmentally controlled, and monitored (manual or automated) area in accordance with the labelled storage conditions with access limited to the Investigator and authorised site staff.

The temperature should be monitored on a daily basis and documented in the temperature monitoring log.

The investigational product must be kept in the original outer container and under conditions specified on the label (between 2 to 8°C (36 to 46°F), protected from the light).

In the following cases, the site staff should not use affected IP and should immediately contact an AstraZeneca representative for further guidance:

- Temperature excursion upon receipt or during storage at the study
- Damaged kit upon receipt
- Damaged syringe/cartridge

Damaged IP should be documented via Interactive Web Response System (IWRS; refer to IWRS manual for further details).

6.2.6. Accountability

The Investigator, institution, or the head of the medical institution (where applicable) is responsible for study treatment accountability, reconciliation, and record maintenance (i.e., receipt, reconciliation, and final disposition records).

An AstraZeneca site monitor will account for all study treatments received at the site, for unused study treatments, and for appropriate destruction or return of unused study treatments. Certificates of delivery, destruction, and/or return should be signed.

In the case of a malfunctioning accessorized prefilled syringe (APFS), the site should contact the study monitor to initiate a product complaint process according to applicable guidelines.

Further guidance and information for the final disposition of unused study treatment are described in the Pharmacy Manual provided to the sites.

6.3. Measures to minimise bias: randomisation and blinding

6.3.1. Methods for assigning treatment groups

Patients will be stratified by region and baseline CCI [REDACTED]. Randomisation will be monitored to ensure that no more than CCI [REDACTED] of the study population will have CCI [REDACTED]. When the target percentage of patients in a subgroup is reached, consideration will be given to closing the IWRS randomisation for that subgroup. Once a subgroup is closed, patients in the screening/run-in period in the closed subgroup will not be allowed to be randomised and will be screen failed. A patient who does not qualify for the open subgroup cannot be rescreened.

All patients will be centrally assigned to randomised study treatment using an IWRS. Before the study is initiated, the log-in information and directions for the IWRS will be provided to each site. The IWRS will provide to the Investigator(s) or pharmacists the kit identification number to be allocated to the patient at the dispensing visit. Routines for this will be described in the IWRS user manual that will be provided to each centre. Randomisation codes will be assigned PPD [REDACTED] in each stratum as patients become eligible for randomisation.

Patients who fail to meet the inclusion/exclusion criteria should not, under any circumstances, be enrolled or receive study treatment. There can be no exceptions to this rule.

If a patient withdraws from the study, then his/her enrolment/randomisation code cannot be reused. Withdrawn patients will not be replaced.

6.3.2. Methods for ensuring blinding

This study includes a 56-week double blind treatment period. AstraZeneca staff involved in the study, the patients, and the Investigators and site staff involved in the treatment of patients or in their clinical evaluation will not be aware of treatment allocation.

Placebo solution will be visually matched with benralizumab solution. Both benralizumab and placebo will be provided in an APFS.

6.3.2.1. Maintaining the blind to the patient's blood and tissue eosinophil counts

While not entirely assured, patients on active benralizumab treatment are expected to have lower blood (or tissue) eosinophil counts than patients on placebo. In order to mitigate potential unblinding on this basis, per protocol haematology will be run by the central laboratory. From baseline (V3) until the second visit of the OLE (Week 60, V12), eosinophil, basophil and monocyte counts will be redacted from all central laboratory reports sent to investigative sites to prevent the Principal Investigator (PI)/designee from possibly deducting the 'eosinophil + basophil + monocyte' contribution to the complete blood count (CBC).

If the Investigator orders any local safety laboratory assessments, the requested tests should be restricted to the question at hand. For example, if haemoglobin (Hb) is desired the Investigator should avoid ordering a complete blood cell count with differential.

6.3.2.2. Handling of labs obtained during the study period but ordered outside of the clinical trial

Site staff who are directly involved in the patient's management should remain blinded to any eosinophil, basophil and monocyte results included as part of outside lab reports. To help ensure this, each investigational site will designate an individual (e.g. administrator or another ancillary person) not directly involved in patient management, from baseline (V3) until the second visit of the OLE (Week 60, V12) to receive and blind any eosinophil, basophil and monocyte results prior to the report being handed over to the site staff involved in the patient's management and prior to filing as a source document. Similarly, eosinophil and basophil results must be redacted from all communications with AstraZeneca.

In cases where the Investigator requires an eosinophil, basophil, or monocyte count for managing safety issues he/she may order these tests. AstraZeneca should be notified of all such cases, but should not be informed about lab results.

6.3.3. Methods for unblinding

Individual treatment codes, indicating the treatment randomisation for each randomised patient, will be available to the Investigator(s) or Pharmacists/designee at the study site from the IWRS. Further detail on how to unblind a patient's treatment allocation will be described in the IWRS user manual provided to each study site.

The randomisation code should not be broken except in medical emergencies when the appropriate management of the patient requires knowledge of the treatment randomisation. The Investigator documents and reports the action to AstraZeneca, without revealing the treatment given to the patient to the AstraZeneca staff.

AstraZeneca retains the right to break the code for SAEs that are unexpected and are suspected to be causally related to an IP and that potentially require expedited reporting to Regulatory Authorities (RAs). Randomisation codes will not be broken for the planned analyses of data (i.e. the primary database lock) until all decisions on the evaluability of the data from each individual patient have been made and documented.

6.3.4. Open-label Extension Period – Benralizumab Administration Only

Patients will keep the same E-code in the OLE as assigned in the double-blind period of the study. Open-label IP administration will begin at Week 56 (V11). The IWRS will continue to allocate IP kit number for each dosing visit of the OLE.

6.4. Treatment compliance

The administration of all study treatments (including IPs) should be recorded in the appropriate section of the eCRF.

The study treatment provided for this study will be used only as directed in this Clinical Study Protocol (CSP). The investigational product will be administered at the study site on treatment visits and within visit windows as specified in the SoA.

If IP cannot be administered at a scheduled treatment visit, it can be postponed as necessary and administered as soon as possible (preferably within visit window). When IP dosing needs to be postponed, it is recommended that all scheduled treatment visit procedures (except for IP administration) are still performed within the visit window.

Re-scheduled IP dose can be then administered at an unscheduled visit. Physical exam and vital signs assessment are the minimum procedures to be performed at this visit. For WOCBP, the urine pregnancy test must be performed; IP will be administered only when the result of the test is negative. It may also include remaining visit procedures (not performed at the scheduled visit) and additional assessments as deemed necessary by the investigator.

If the visit procedures cannot be conducted within the window (e.g. the patient is unable to attend the study site), then the entire visit will be re-scheduled along with IP dosing.

If a dose is significantly delayed it is recommended to keep at least 2-4 weeks interval before the next dose. If a postponed dose overlaps with the next treatment visit window, the postponed dose will be skipped, and the next dose of IP given at the regularly scheduled visit. The visit schedule will be always calculated from randomisation visit date.

Any change from the dosing schedule, dose interruptions, dose discontinuations should be recorded in the eCRF.

The PI should make every effort to assure that no IP administrations are missed during the course of the study. If a patient misses more than 2 consecutive or non-consecutive doses of IP at any time within a calendar year, it is strongly recommended a conversation between the investigator and the AZ study physician to review the patient's adherence to treatment and decide on the patient's disposition. Before a decision to discontinue a patient from IP is instituted, the investigator should carefully consider whether continuation on IP or discontinuation of IP will be in the best interest of the patient, and whether the issue can be mitigated by postponing or skipping the dose. It is highly recommended that the AZ study physician be consulted before the IP discontinuation transaction takes place. In case of safety concerns IP administration may be immediately withheld until the final decision is made.

Principal Investigators should also assure that patients are compliant and on a stable dose of the background medication during study period.

The site staff is responsible for managing the Investigational medicinal product (IMP) from receipt by the study site until the destruction or return of all unused IMP.

6.5. Concomitant therapy

The Investigator must be informed as soon as possible about any medication taken from the time of screening until the end of the study. Any concomitant medication(s), including herbal preparations, taken during the study will be recorded in the eCRF, along with

Reason for use

Dates of administration including start and end dates

Dosage information including dose and frequency

List of the restricted and prohibited medication can be found in [Table 7 Restricted medications](#) and [Table 8 Prohibited medications](#) , provided below:

Table 7 Restricted medications

Medication/class of drug:	Usage (including limits for duration permitted and special situations in which it's allowed):
LTRA (until V11 week 56)	LTRA is allowed if stable for minimum 30 days prior to V1 and maintained stable
Inactive/killed vaccinations (e.g. inactive influenza)	Not allowed within the 7 days before or within 7 days after any IP dosing study visit
Topical immunosuppressives (until V11 week 56)	Topical administration of Immunosuppressive medication may be allowed at the discretion of the Investigator
Allergen Immunotherapy	Allowed if on stable therapy started 30 days prior to V1; no change during the treatment period until the last study visit
Systemic corticosteroids (SCS) (until V11 week 56)	A short course of SCS (≤ 17 days), allowed at PI's discretion to relieve symptoms of nasal polyposis worsening or asthma exacerbations, but preferably not until 3-6 months after randomization. It is recommended not to use SCS for CRSwNP within the first 3-6 months after V3. Refer to Section 8.1.5 for details.
Decongestants (topical or systemic) (until V11 week 56)	Only allowed for endoscopic procedure

Table 8 Prohibited medications

Prohibited medication/class of drug:	
Intranasal medication including intranasal corticoids drops (until V11 week 56)	Only MFNS (400 mcg daily) or equivalent (highest local approved for CRSwNP) is allowed and should remain stable.
Any immunosuppressive treatment including but not limited to: methotrexate, cyclosporine, mycophenolate, tacrolimus, gold, penicillamine, sulfasalazine, hydroxychloroquine, azathioprine, cyclophosphamide	Not allowed within 3 months prior to V1; during the study period and 3 months after last dose of the IP.
Aspirin desensitization (including OLE period)	Use of aspirin as a desensitization regimen for the management of aspirin exacerbated respiratory disease (AERD) is not allowed; all other uses of aspirin/NSAID is allowed for any other medical conditions.
Any marketed or investigational biologic (monoclonal or polyclonal antibody) (including OLE)	Not allowed within 6 months or 5 half-lives (whichever is longer) prior to V1; during the study period and 4 months or 5 half-lives (whichever is longer) after the last dose of IP.
Other investigational product	Not allowed within 30 days or 5 half-lives (whichever is longer) prior to randomisation; and during the study period until the last study visit.
Live attenuated Vaccines	Not allowed within 30 days prior to randomisation; during the study period, and 12 weeks or 5 half-lives (whichever is longer) after the last dose of the IP.
Blood products or immunoglobulin therapy	Not allowed within 30 days prior to V1 and during the study period until the last study visit.
Herbal remedies or traditional Chinese medicines that may impact nasal polyps or its symptoms as per investigators judgement (until V11 week 56) - for Asia only	Not allowed 30 days prior to V1 and during the treatment period.

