5.1. Inclusion criteria

Subjects are eligible to be included in the study only if all of the following inclusion criteria and none of the exclusion criteria apply:

Informed consent

1. Capable of giving signed informed consent which includes compliance with the requirements and restrictions listed in the informed consent form (ICF) and in this protocol.

2. Provision of signed and dated, written informed consent form prior to any mandatory study specific procedures, sampling, and analyses.
3. Provision of signed and dated written Genetic informed consent prior to collection of sample for genetic analysis.

The ICF process is described in Appendix A 3.

Age

4. Subject must be 18 to 75 years of age inclusive, at the time of signing the informed consent form.

Type of patient and disease characteristics

5. Patients with bilateral sinonasal polyps that, despite treatment with a stable daily dose of INCS for at least 4 weeks prior to V1, in addition to a history of treatment with SCS (oral, parenteral) and/or prior surgery for CRSwNP have severity consistent with a need for surgery as described by:
 - A minimum total NPS of 5 out of a maximum score of 8 (with a unilateral score of at least 2 for each nostril) at V1 and continuously maintained at V2 to meet the randomisation criterion as determined by the study Imaging Core Lab.
 - Ongoing symptoms for at least 12 weeks prior to V1.
 - Patient-reported moderate to severe nasal blockage (score 2 or 3) over the 2-weeks prior to V1 (2-week recall assessment of symptoms, scores 0-none to 3-severe).
6. A documented physician-diagnosed asthma.
7. Asia only (Japan, China Mainland, China Taiwan, Vietnam, and Thailand): CT Lund Mackay score for ethmoid \geq maxillary at V2, as determined by the study Imaging Core lab .
8. Blood eosinophil count of $>2\%$ or $\geq 150/\mu\text{L}$ at V1, as determined by central lab. The test may be repeated once based on the Investigators medical judgement.
9. Patients who are on leukotriene receptor antagonists (LTRAs), need to be at stable dose for at least 30 days prior to V1.
10. Willingness to maintain all standard of care treatment for CRSwNP stable for the duration of the study.
11. SNOT-22 total score ≥ 20 at enrolment (V1).

Patient must meet the following criteria at the randomisation visit (V3):

12. At least 8 days of evaluable daily diary data in the 14-day period prior to randomisation (baseline bi-weekly mean score collected from study Day -13 to study Day 0).

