6.5.1. Background medication

During the study, the background INCS will be MFNS. Patients not already using MFNS will be converted to MFNS at 400 mcg daily or equivalent (highest dose locally approved for CRSwNP) if MFNS is not available locally at visit 1. All patients are required to be stable on background INCS for a minimum of 4 weeks prior to V2, continued throughout the screening and study period until V11 (week 56).

MFNS (50 micrograms/actuation) nasal spray is contained in a bottle that contains 120 actuations for US and 140 actuations for all other countries. Two doses (50 mcg/actuation) in each nostril twice daily (total daily dose of 400 mcg) will be administered, unless there is a

medical rationale to use the lower dose (QD) regimen. Any change in background medication should be discussed with the AZ study physician, the justification should be documented in the source and the change in the doses should be reflected in the eCRF.

Each patient will receive enough background medication to cover the need until the next on site visit. INCS dispensation will be performed according to the SoA table (Table 1 and 2).

INCS compliance will be recorded by the patient on the ePRO device (using NPSD) and should be checked by Investigators during the study period until V11 (week 56). If a subject cannot tolerate MFNS during screening period, the subject should be screen failed.

Patients in Japan will follow the requirement regarding to INCS use as indicated in the country protocol.

The Principal Investigator should ask patients about SCS (oral, parenteral) use for CRSwNP at each visit and record in the eCRF. If deemed necessary and medically justified, a short course of SCS (≤ 17 days) is allowed for CRSwNP worsening during the study, at PI's discretion but adequately documented, according to local standard of care. If SCS is used for ≤ 17 days between V1 and V2, the screening may be extended for maximum 6 more weeks. Otherwise, patient should be screen failed, but can be considered for rescreening once (please refer to section 5.5.1 Re-screening).

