8.1.1.6. Asthma exacerbations

Asthma exacerbation is defined by a worsening of asthma requiring:

- Use of systemic corticosteroids for at least 3 days; a single depo-injectable dose of corticosteroids will be considered equivalent to a 3-day course of systemic corticosteroids,
- An emergency room/urgent care visit (defined as evaluation and treatment for < 24 hours in an Emergency department or urgent care centre) due to asthma that required systemic corticosteroids (as per above),

- An inpatient hospitalization due to asthma (defined as an admission to an inpatient facility and/or evaluation and treatment in a healthcare facility for ≥ 24 hours),
- Use of systemic corticosteroids (oral, parenteral), an emergency room/urgent care visit or a hospitalisation due to asthma should be recorded in the corresponding eCRF. A hospitalisation should also be reported as an SAE.

The start date of an exacerbation is defined as the start date of systemic corticosteroid administration or date of hospital admission due to asthma. The end date of an exacerbation is defined as the last day of systemic corticosteroids or date of hospital discharge. A subsequent exacerbation must be preceded by at least 7 days in which neither criteria is fulfilled.

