8.1.5. SCS use for CRSwNP

Patients who have a scheduled SCS use at the time of the study enrolment and randomisation should not be randomised in the study (please refer to [exclusion criterion 22](#)). After randomisation, patients are not recommended to use SCS for CRSwNP for the first 3 to 6 months unless emergent or deemed necessary by the PI. These cases should be discussed with the AZ study physician. Investigators need to record the medical justification for SCS use in source data. Safety and efficacy (including total NPS, SNOT-22, SF-36v2, PGI-S, PGI-C, ACQ-6 and UPSIT) assessment should be performed prior to the SCS use for CRSwNP.

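### The systemic corticosteroid row of Table 7 disagrees with itself and with Section 8.1.5 on whether the advice to wait 3 to 6 months covers asthma exacerbations

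*Protocol*

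**What the plan says.** Four places in the protocol deal with SCS after randomisation.

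- **Table 7, SCS row, first sentence (Section 6.5).** A course of up to 17 days is "allowed at PI's discretion to relieve symptoms of nasal polyposis worsening or asthma exacerbations, but preferably not until 3-6 months after randomization". Two indications are named, and one timing preference follows them.
- **Table 7, SCS row, second sentence.** "It is recommended not to use SCS for CRSwNP within the first 3-6 months after V3". Only CRSwNP is named. The cell then sends the reader to Section 8.1.5.
- **Section 8.1.5.** "patients are not recommended to use SCS for CRSwNP for the first 3 to 6 months unless emergent or deemed necessary by the PI". Again only CRSwNP is named, now with an exception.
- **Section 6.5.1.** A short course "is allowed for CRSwNP worsening during the study, at PI's discretion but adequately documented, according to local standard of care". Only CRSwNP worsening is named, and no early period is singled out.

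Inclusion criterion 6 (Section 5.1) requires asthma: "A documented physician-diagnosed asthma". Section 8.1.1.6 defines an asthma exacerbation by three routes. The first is "Use of systemic corticosteroids for at least 3 days", the second is an emergency or urgent care visit that needed SCS, and the third is an inpatient hospitalisation for asthma. SAP Section 3.7.2 follows the same structure.

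**The concern.** The restricted-medication table is where a site looks first when a patient needs SCS. For a patient with an asthma exacerbation a few weeks after randomisation, the first sentence of the row says that SCS is preferably avoided at that stage. The second sentence and Section 8.1.5 suggest that the advice was meant only for polyp disease. Different sites could settle this differently.

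Two things are at stake. The first is how consistently, and how safely, acute asthma is handled in a population selected for having asthma. The second is measurement: two of the three routes to a counted exacerbation require SCS. An event treated without SCS because of the row, and not leading to admission, would not enter the exacerbation rate.

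**Working it through.** **Step 1: the texts side by side.**

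| Place (Protocol) | Indication covered | Early timing advice | Exception stated |
|---|---|---|---|
| Table 7, first sentence | Polyp worsening and asthma exacerbation | Preference to wait 3–6 months | Investigator discretion in general |
| Table 7, second sentence | CRSwNP | Recommendation to wait 3–6 months | None; refers to 8.1.5 |
| Section 8.1.5 | CRSwNP | Recommendation to wait 3–6 months | Emergent, or judged necessary by the investigator |
| Section 6.5.1 | CRSwNP worsening | None | Not applicable |
| Section 8.1.1.6 | Asthma exacerbation (definition and recording) | None | Not applicable |

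The first row is the only one that attaches timing advice to asthma. If its first sentence was meant for CRSwNP alone, the second sentence adds nothing to it. If it was meant for both indications, the second sentence and Section 8.1.5 leave one out.

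**Step 2: does anything else settle it?** Section 6.5.2 leaves other medication to the investigator, but only medication not already described, and SCS is described. Section 8.1.5 is confined to CRSwNP by its title as well as its text, so its exception is not written for asthma. Section 8.1.1.6 says how to define and record an exacerbation and nothing about when SCS may be given. The asthma case stays open.

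**Step 3: the 17-day limit.** Table 7 applies it to both indications. Section 5.5.1 does the same during screening. Section 6.5.1 uses it for CRSwNP. No place gives a different limit for asthma, so there is no conflict here.

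**Step 4: length of the window.** The double-blind period is 56 × 7 = 392 days.

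- 3 months: 3 × 365.25/12 = 91.3 days; 91.3/392 = 23.3%.
- 6 months: 6 × 365.25/12 = 182.6 days; 182.6/392 = 46.6%.

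The exacerbation rate is analysed over the whole double-blind period (SAP Section 4.2.9.2), so the window lies inside it.

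**Step 5: what under-counting would do.** Let w be the window's share of follow-up and f the fraction of early exacerbations left uncounted. Assume constant event rates λ_B (benralizumab) and λ_P (placebo), and the same f in both arms. The counted rate in each arm is then λ(1 − wf).

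- Rate ratio: λ_B(1 − wf) / [λ_P(1 − wf)] = λ_B/λ_P, unchanged.
- Rate difference: (λ_P − λ_B)(1 − wf), smaller by the factor 1 − wf.

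The planned negative binomial model with a log follow-up offset is multiplicative, so its rate ratio would stay about the same. It would move if f differed between arms, or if the early and late rate ratios differed. The documents give no value for f.

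**Step 6: reach into the confirmatory analysis.** The intercurrent events in the primary estimand are surgery for CRSwNP, SCS for CRSwNP and treatment discontinuation (SAP Section 4.1.4.1). SCS for asthma is not listed. The exacerbation rate is exploratory (Protocol Table 4) and outside the testing hierarchy (Protocol Section 9.4.4).

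**The case against.** The strongest reply is that the cell corrects itself. Its second sentence restates the advice for CRSwNP alone and sends the reader to a section limited to CRSwNP. The first sentence only states a preference and leaves the decision to the investigator. The protocol plainly expects SCS to be given for asthma: it defines exacerbations by it, asks for it to be recorded, and does not list it as a reason to stop study treatment. Much of this stands. A reader might infer that Table 7 forbids SCS for early asthma exacerbations, and the text does not support that. What does not stand is that the ambiguity disappears: two adjacent sentences differ in scope, and neither is marked as governing.

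A reader might also infer that Sections 6.5.1 and 8.1.5 give a contrary instruction for asthma. They do not; they are silent on SCS for an on-study exacerbation. The conflict lies in the scope of the timing advice.

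A third reply concerns timing. The SAP amendment history dates protocol version 5.0 to 6 May 2024, and the synopsis expects the last patient to complete in Q4 2025. If that patient follows the full 112-week schedule, randomisation fell in about August to November 2023, and the early window had closed or nearly closed by version 5.0. This is an inference, and a late patient who does not enter the extension would change it. It limits the practical effect of a correction but does not make the text consistent.

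**Conclusion.** The inconsistency is real and sits mainly within one table cell. Its first sentence covers asthma exacerbations; its second sentence and Section 8.1.5 do not, and no other section resolves the asthma case. Because asthma is required at entry, the situation it leaves unclear is one that sites can expect to meet. The main reason to act is clarity of instruction on acute asthma treatment.

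The statistical consequence is secondary and modest. It touches an exploratory rate, asthma hospitalisations count without SCS, and equal proportional under-counting would leave the rate ratio about unchanged under the assumptions of step 5. A reader might infer that a definite share of exacerbations will be lost, or that the treatment effect on exacerbations will be diluted. Either claim needs a fraction of early events treated without SCS, and the documents offer no basis for one. The only supported figure is the window itself, about 23–47% of the double-blind period. No effect on the co-primary or key secondary endpoints is shown.

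**What to change.** Reconcile Table 7 with Sections 6.5.1 and 8.1.5. Make the two sentences of the SCS cell agree, most simply by splitting the row into SCS for CRSwNP and SCS for asthma exacerbation. State for each whether the early-timing advice applies, and carry the same wording into Sections 6.5.1 and 8.1.5. The sponsor's clinical team decides the content; this review takes no position on which rule is right. Send sites a short clarification.

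The cost is one table row, matching edits in two sections and a site letter. No procedures, visits, patients or analyses change.
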